2.2.13.3.1 Serious Adverse Events

The number and percentage of subjects experiencing a Serious Adverse Event (SAE) will be tabulated by SOC and PT within each treatment group and overall. SAEs will be counted only once for a subject within each PT and SOC.

2.2.13.3.2 Deaths

A listing of subjects who die while on study will be prepared along with the adverse event associated with the cause of death.

2.2.13.3.3 Interruptions or Discontinuations of Study Medication Due to an AE

A listing of subjects who have changes to their study medication dosing (dose reduced, interruptions or discontinuations) will be prepared.

2.2.13.4 Laboratory Data

Any laboratory test results considered to be clinically significant by the Investigator will be captured as an adverse event. All clinical laboratory values (haematology and biochemistry) will not be tabulated but will be listed for each patient by treatment group and visit. Values outside the laboratory normal ranges will be listed separately by patient and treatment group with associated comments as to their clinical significance.

2.2.13.5 Vital Signs, Physical Findings, and Other Observations Related to Safety

Vital signs are collected at the screening, visit 2/baseline and the follow-up visits. Temperature (°C), systolic and diastolic blood pressure (mmHg) and heart rate (BPM) will be tabulated by treatment group using the baseline value (where baseline record flag= 'Y') and end of study (week 10). Change from end of study to baseline will be presented as descriptive statistics.

Physical Examination Findings will be presented in the listings but not tabulated.

Concomitant Medications will be coded per the WHO Drug dictionary (version effective March 2017 and provided to CTDS in the SDTM CM dataset). Concomitant Medications will be tabulated by treatment group, Drug Class (pharmacological level, ATC3) and Drug Name (chemical substance level, ATC5). These data will be provided in subject data listings along with the verbatim drug term and usage details.

3 Document Version Control

Revision History:

REVISION	RELEASE DATE	AUTHOR	SUMMARY OF CHANGES
A	17Jul2017	CTDS/[name]	Initial Version

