8.2.7 Week 8 (Visit 6) / End of Treatment or Early Termination

Patients will return to the investigational site at Visit 6. **The last dose of DS107/Placebo should be taken the day before Visit 6.**

For accountability purposes, patients will be required to bring both the used DS107/Placebo patient packs and unused DS107/Placebo supplied at Visit 5. Patients will be required to provide the patient compliance log for confirmation of compliance.

The following procedures/assessments will occur:

- Samples for clinical laboratory safety tests (haematology, serum biochemistry, urinalysis as detailed in Section 9.2.4)
- Pharmacokinetic Sampling (as detailed in Section 9.2.7)
- Biomarker Sampling (as detailed in Section 9.2.8)
- Sample for pregnancy test (only female patients of child-bearing potential, as detailed in Section 9.2.5)
- Vital signs (blood pressures, heart rate and body temperature), as detailed in Section 9.2.3);
- Physical examination (as detailed in Section 9.2.2)
- Body Mass Index (as detailed in Section 9.2.6)
- Collect Study Drug
- Collect and Review Patient Compliance Log
- IMP Accountability (as detailed in Section 10.6)
- Body Surface Area (as detailed in Section 9.1.4)
- Investigator's Global Assessment (as detailed in Section 9.1.1)
- Eczema Area and Severity Index (EASI) (as detailed in Section 9.1.2)
- NRS Pruritus assessment (as detailed in Section 9.1.3)
- Dermatology Life Quality Index (DLQI) Questionnaire (as detailed in Section 9.1.5)
- Patient Orientated Eczema Measure (as detailed in Section 9.1.6)
- Patient Global Impression of Severity Questionnaire as detailed in Section 9.1.7)
- Patient Global Impression of Change Questionnaire as detailed in Section 9.1.8)
- Concomitant medication assessment (as detailed in Section 9.2.11)
- AE assessment (as detailed in Section 11)

The DS107or Placebo patient packs will be returned. No further DS107or Placebo patient packs or patient compliance logs will be issued. Following completion of the study assessments at this visit, there will be continued study restrictions in line with those described in sections 9.2.11 and 9.2.12.

An NRS for the assessment of pruritus will continue to be captured on a daily basis from baseline to the follow up visit. Emollient use will also continue to be captured on a daily basis for the same period.

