8.2.8 Week 10 (Visit 7) / Follow up

Two weeks after Visit 6 (or early withdrawal visit), patients will return to the investigational site and the final procedures/assessments will occur:

- Samples for clinical laboratory safety tests (haematology, serum biochemistry, urinalysis as detailed in Section 9.2.4) - Only if clinically significant change from baseline in safety lab results at Week 8 / Visit 6
- Pharmacokinetic Sampling (as detailed in Section 9.2.7)
- Vital signs (blood pressures, heart rate and body temperature), as detailed in Section 9.2.3);

- Physical examination (as detailed in Section 9.2.2)
- Body Surface Area (as detailed in Section 9.1.4)
- Investigator's Global Assessment (as detailed in Section 9.1.1)
- Eczema Area and Severity Index (EASI) (as detailed in Section 9.1.2)
- NRS Pruritus assessment (as detailed in Section 9.1.3)
- Dermatology Life Quality Index (DLQI) Questionnaire (as detailed in Section 9.1.5)
- Patient Orientated Eczema Measure (as detailed in Section 9.1.6)
- Patient Global Impression of Severity Questionnaire as detailed in Section 9.1.7)
- Patient Global Impression of Change Questionnaire as detailed in Section 9.1.8)
- Concomitant medication assessment (as detailed in Section 9.2.11)
- AE assessment (as detailed in Section 11)

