9.2.3 Vital Signs

Vital signs measurements will be performed as per the Study Flow Chart (Appendix 1) at every visit. Measurements to be taken include:

- Blood pressure: will be performed as supine (after at least 5 minutes of rest) systolic and diastolic blood pressure (in mmHg)
- Heart rate: taken at rest (in bpm)
- Temperature: will be taken as per clinic practice. Temperature and route will be recorded in the CRF.

Vital signs measurements will be performed before any blood samples are taken. All new findings or changes to previous findings considered clinically significant will be recorded in the CRF as an AE if the finding is made after the patient has signed the ICF.

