12.8 Safety Analysis

Demographic, medical history and physical examination data will be listed for each patient and summarised descriptively.

All AEs recorded during the study will be coded to system organ class and preferred terms using the current version of the Medical Dictionary for Regulatory Activities (MedDRA). AEs will be tabulated and summarised by treatment, relationship to treatment and severity.

Clinical laboratory values (haematology, biochemistry, and urinalysis) will be listed for each patient by treatment and day. Values outside the laboratory normal ranges will be listed separately with associated comments as to their clinical significance, with potentially clinically significant abnormalities highlighted and summarised by treatment. Clinical laboratory values obtained prior to dosing will be defined as baseline values.

Individual values of vital signs will be listed and summarised descriptively for each treatment and day.

Concomitant medications (if any), categorised by medication group and subgroup according to the latest version of the World Health Organisation drug dictionary, will be listed and summarised by treatment.

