Secondary Endpoint(s)	
 • Proportion of patients achieving an IGA score of 0 (clear) or 1 (almost clear) and a decrease of at least 2 points in IGA in treated population compared to placebo population from baseline to Week 2, 4, 6 and 10. • Proportion of patients achieving a decrease of at least 2 points in IGA in treated population compared to placebo population from baseline to Week 2, 4, 6, 8 and 10. • Change from baseline in Eczema Area and Severity Index (EASI) in treated population compared to placebo population at Weeks 2, 4, 6, 8 and 10. • Change from baseline in Numeric Rating Scale (NRS) for Pruritus in treated population compared to placebo population at Weeks 2, 4, 6, 8 and 10.
Exploratory Endpoints	
 • Time to response by Week 8. • Probability of being in response (PBIR) between Weeks 2 and 8. • Sustained efficacy between Weeks 8 and 10. • Change from baseline in the Dermatology Life Quality Index (DLQI) score in treated population compared to placebo population at Week 2, 4, 6, 8 and 10 and from Week 8 to Week 10.

	
 • Change from baseline in the Patient Orientated Eczema Measure (POEM) score in treated population compared to placebo population at Week 2, 4, 6, 8 and 10 and from Week 8 to Week 10. • Change from baseline in the Patient Global Impression of Severity (PGI-S) score in treated population compared to placebo population at Week 2, 4, 6, 8 and 10 and from Week 8 to Week 10. • Change from baseline in the Patient Global Impression of Change (PGI-C) score in treated population compared to placebo population at Week 2, 4, 6, 8 and 10 and from Week 8 to Week 10. • Plasma DGLA concentrations in treated population compared to placebo population at Baseline/Day 0, Week4, Week 8 and Week 10 (samples to be retained for the potential analysis at a later date). • Determination of AD biomarkers in treated population compared to placebo population at Baseline/Day 0 and Week 8/Early Termination (samples to be retained for the potential analysis at a later date).
Safety Endpoints	
 • Adverse event (AE) and serious adverse event (SAE) frequency and severity. • Safety laboratory parameters (haematology, clinical chemistry). • Clinical safety examinations (vital signs, physical examination).

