2.1 General Considerations

The objective of this double-blinded Phase 2b study is to assess the efficacy and safety of orally applied DS107 to adults with moderate to severe Atopic Dermatitis. This study uses a randomized (1:1:1, Treatment group A: 1g DS107, Treatment group B: 2g DS107 and Treatment group C: Placebo), double-blind, placebo-controlled parallel group design. Disposition, compliance, demographics, and primary and secondary efficacy results will be presented by treatment group separately for moderate and severe AD as well as for combined groups.

Study medication will be orally applied once daily for 8 weeks. An End of Therapy (EOT) visit will occur at Week 8 for subjects who complete 8 weeks of treatment or earlier if the subject discontinues from the study prematurely. An End of Study (EOS) visit will be conducted at 10 weeks post-treatment for all subjects, even if they withdrew early. For subjects who discontinue early, they will also be asked to return two weeks later for the safety assessments listed at Week 10/Visit 7.

All subjects screened into the study will be assigned a patient identifier number during screening that will be used on all patient documentation. The patient identifier number will contain the site number and the patient number assigned in numerical order at the screening visit (e.g.: 102-10 for the tenth patient screened at the site number 102). Patient numbers will be assigned in ascending order starting with 01. All data will be listed in subject data listings sorted by site and subject number unless otherwise noted. Data tabulations will be prepared as described in the sections below.

All statistical processing will be performed using Statistical Analysis System (SAS®) Version 9.3 or higher, unless otherwise noted. All analyses will be conducted in accordance with ICH E6 and E9 standards and applicable Contract Research Organisation (CRO) Standard Operating Procedures (SOPs). CDISC and SDTM data conventions will be followed; these data sets will include DLQI scoring performed by the data management group and provided to CTDS in the SDTM datasets.

The 2g DS107 treatment group will be tested against the placebo group using a hierarchical approach and if significant at the 0.05 level, then the 1g DS107 treatment group will be tested against the placebo at the 0.05 level, otherwise these will be presented as descriptive statistics.

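### The SAP tabulates vital signs by arm only at baseline and Week 10, nominally 15 days after the last dose, although the protocol promises a descriptive summary for every treatment and day

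*SAP*

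**What the plan says.** The protocol schedules the measurements throughout the study. Section 9.2.3 states: "Vital signs measurements will be performed as per the Study Flow Chart (Appendix 1) at every visit". The flow chart in Appendix 1 agrees, giving screening, Day 0 and Weeks 2, 4, 6, 8 and 10. Section 12.8 then commits to the reporting: "Individual values of vital signs will be listed and summarised descriptively for each treatment and day".

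The SAP names vital signs among its safety endpoints in section 1: "Clinical safety examinations (vital signs, physical examination"). Section 2.2.13.5 acknowledges that they are collected at the follow-up visits, but says that they "will be tabulated by treatment group using the baseline value (where baseline record flag= 'Y') and end of study (week 10"). It adds one descriptive change, between those two time points.

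Two further provisions matter. SAP section 2.1 provides: "All data will be listed in subject data listings sorted by site and subject number unless otherwise noted". Protocol section 9.2.3 provides: "All new findings or changes to previous findings considered clinically significant will be recorded in the CRF as an AE".

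On timing, protocol section 8.2.7 states: "The last dose of DS107/Placebo should be taken the day before Visit 6". Section 8.2.8 places the last visit afterwards: "Two weeks after Visit 6 (or early withdrawal visit), patients will return to the investigational site".

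**The concern.** The SAP drops a summary that the protocol promises, gives no reason, and keeps the one post-baseline visit at which a treatment completer is no longer taking capsules. The trial compares two doses with placebo, and SAP section 2.2.7 plans no safety monitoring committee, so the final tables carry the safety comparison between arms.

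A change judged clinically significant in a patient becomes an adverse event and is tabulated by arm. A smaller mean shift in blood pressure or heart rate during dosing, not judged significant in any one patient, would appear in no table. It would sit in line listings for about 300 patients sorted by site and subject, which are not a summary by arm. The documents give no offset time for DS107, so it is unknown whether such a shift would still be visible at Week 10.

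Patients who withdraw completely and miss Visit 7 would contribute no post-baseline value to the table, even if they had readings at earlier visits.

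**Working it through.** **Which visits are summarised.** Post-baseline visits with vital signs (protocol Appendix 1): Days 14, 28, 42, 56 and 70, so 5. Tabulated in SAP 2.2.13.5: Day 70, so 1. Omitted: Days 14, 28, 42 and 56, so 4 of 5. The first three fall during dosing and Day 56 falls one day after the nominal last dose.

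**Does another part of the SAP restore them?** No.
- Section 2.2.12 promises by-visit summaries, but for efficacy endpoints.
- Section 2.1 gives listings only.
- Appendix A sets format only.
- The contents list shows no section on departures from the protocol.

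**Time from last dose to the tabulated visit.** Inputs: Visit 6 on Day 56 ± 2 and Visit 7 on Day 70 ± 3 (SAP 2.2.5, protocol Appendix 1); last dose the day before Visit 6 (protocol 8.2.7).
- Check of the plan's own interval: 70 − 56 = 14 days, which reproduces the stated two weeks.
- Nominal last dose: 56 − 1 = Day 55. Nominal gap: 70 − 55 = 15 days.
- Visit 7 timed from the actual Visit 6, with ± 3 days: 14 + 1 − 3 = 12 days to 14 + 1 + 3 = 18 days.
- Both windows varying independently: last dose on Day 53 to 57 and Visit 7 on Day 67 to 73, so 67 − 57 = 10 days to 73 − 53 = 20 days.
- Product stopped early with visits continued (protocol 7.5.2) and Visit 7 kept at Day 70: a last dose on Day 28 gives 70 − 28 = 42 days; a last dose on Day 14 gives 70 − 14 = 56 days.

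SAP 2.1 describes the end-of-study visit as ten weeks after treatment, which conflicts with Day 70 in SAP 2.2.5 and in the flow chart. Day 70 is used here.

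**Precision of a by-visit comparison (illustration only).** The documents give no SD, so an SD of systolic change of 8 to 14 mmHg is assumed. With 100 patients per arm and no dropout, the 95% half-width for a difference between two arms at one visit is 1.96 × SD × √(2/100):

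| Assumed SD (mmHg) | Half-width (mmHg) |
|---|---|
| 8 | 2.22 |
| 10 | 2.77 |
| 12 | 3.33 |
| 14 | 3.88 |

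**Related departures from protocol 12.8.**
- *Laboratory (secondary).* The protocol promises a summary by treatment of potentially clinically significant abnormalities; SAP 2.2.13.4 lists laboratory values without tabulating them. Results the investigator considers clinically significant become adverse events, which covers the promise only in part, and the SAP does not say that this is meant to satisfy it.
- *Physical examination (note only).* The protocol promises a descriptive summary; SAP 2.2.13.5 lists findings only. Protocol 9.2.2 makes the examination symptom-directed and records changes as adverse events, so little is lost.

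**The case against.** The strongest reply is that little depends on the missing table. Every value is listed, significant changes are tabulated by arm as adverse events with Fisher tests, and protocol 1.6 reports no drug-related adverse events associated with vital signs in the earlier oral study. No hypothesis, stopping rule or dose decision in the documents rests on these tables, and they could be produced at reporting without any alpha cost. Protocol 12.6 also leaves the detailed description of analyses to the SAP. This is fair on consequence and keeps the point from being critical. It does not explain why a stated summary was dropped, and leaving detail to the SAP is not the same as withdrawing a commitment.

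Three narrower objections deserve an answer.

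- **The precision figures do not measure the defect.** The SD is assumed, and a descriptive table would not report an interval between arms. A true shift equal to the half-width would give an interval excluding zero only about half the time. The figures show the scale of mean difference that by-visit data could inform, and nothing in the conclusion rests on them.
- **The 42- and 56-day gaps depend on one reading.** SAP 2.2.5 puts Visit 7 at Day 70 for all subjects, which supports them. Protocol 8.2.8 instead times it from the early withdrawal visit, which could make the gap much shorter. They are possible cases, not typical ones.
- **A by-visit table would include patients who stopped product but kept attending.** True. The SAP already analyses by nominal visit, and the table would still describe the randomised treatment period far better than Week 10 alone.

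**Conclusion.** The concern holds. Followed as written, SAP 2.2.13.5 contradicts protocol 12.8 and leaves 4 of 5 post-baseline visits without a summary by arm for a named safety endpoint. For treatment completers the only post-baseline table is nominally 15 days after the last dose: 12 to 18 days if Visit 7 is timed from the actual Visit 6, and 10 to 20 days if the windows vary independently. This rests on the Day 56 and Day 70 visits and on the last dose being taken the day before Visit 6 as instructed.

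The loss is a promised descriptive safety summary. There is no known signal, individual data are not lost, and no efficacy analysis is affected. The plan should be corrected, and the correction is simple.

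**What to change.** **SAP 2.2.13.5, vital signs.** State that temperature, systolic and diastolic blood pressure and heart rate will be summarised by treatment group at baseline and at Weeks 2, 4, 6, 8 and 10, with change from baseline at each post-baseline visit, descriptively and without p-values. Define change as visit value minus baseline, as in SAP 2.1; the present wording runs it from end of study to baseline, which reverses that definition. Say how early termination values are placed, since SAP 2.2.5 treats an early end-of-treatment visit as Visit 6.

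**SAP 2.2.13.4, laboratory.** Either add the number and percentage of patients per arm with a potentially clinically significant abnormality at Week 8/Early Termination, with criteria fixed before unblinding because neither document defines them, or state that the adverse event route is meant to satisfy protocol 12.8.

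**Physical examination.** State that findings are listed only, and why this departs from protocol 12.8.

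**Cost.** SAP wording, one set of standard by-visit tables, and one laboratory count table or one sentence. All the data are already collected, and by-visit summaries are already planned for the efficacy endpoints.

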Appendix A - Programming Specifications for Tables and Listings

The following specifications will be used in the production of tables and listings.

1. Page Setup

Unless otherwise noted, tables and listings will use landscape orientation. Margins will be at least 1.5 inches on the bound side and at least 1 inch on the other three sides.

The following header information should be included:

- Upper left: Sponsor name and protocol number
- Center: CONFIDENTIAL
- Upper right: Page number shown as Page n of N. Page numbers should be sequential within a table or listing.

The footer should include:

- The name of the SAS program used to generate the output along with the run date/time and the words “by CTDS”.
- For tables, the corresponding listing number(s).

2. Footnotes

Unless otherwise specified, footnotes should appear on all pages within the table.

3. Font

Font will be 8-point Arial, or smaller if needed for space constraints. If possible, small tables should appear on one page. If tables continue on to multiple pages, there should be a page break after an assessment so that all the statistics for an assessment appear on the same page.

4. Tables

Table titles should reflect the content of the table. Under the main title, in parentheses, the name of the analysis population being summarized should appear.

4.1 Summary Statistics - Continuous Data

Unless otherwise noted, the mean and median and confidence interval (CI) of a set of values should be printed out to one decimal place more than the original value. The standard deviation should be printed out to 2 decimal places more than the original value. The number of subjects on whom the parameter is assessed should appear. Minimum and maximum should be consistent with the original value. P-values will be expressed as 4 decimal places. Any p-values that get calculated as 0.0000 should be expressed as p-value <0.0001.

4.2 Summary Statistics - Categorical Data

Numbers of subjects are reported as whole numbers. Null counts are represented as 0. Table percentages should be reported to one decimal unless otherwise noted. Null percentages should be reported as 0.0%.

For all categories, the total number of subjects with data will be presented as N and the number of subjects with non-missing data will be used as the denominator for the calculation of the percentages, unless otherwise noted.

5. Subjects Included in Listings

In general, subject data listings should include all subjects who signed the informed consent. If a listing includes a subset of subjects who meet a certain condition (eg, subjects with SAEs) then this should be clear from the title of the listing. If there are no subjects who meet the condition (eg, no subjects with SAEs) for either the tables or the listings, then a page marker should appear stating that no subjects met the criteria.

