Overall, DS107 capsules administered to 48 healthy volunteers as a single 500mg, 1g, 2g, or 4g dose under fasted conditions; as a single 1g dose under fed conditions; and as multiple 2g and 4g doses taken once daily for 28 consecutive days was well tolerated.

DS107 Capsules Phase 2a Study

This 8 week study was a randomized, placebo-controlled, double-blind, multi-centre Phase 2a trial to investigate the efficacy, safety, tolerability and bioavailability of 2g DS107 administered orally once daily versus 2g placebo administered orally once daily in adult patients with moderate to severe AD. The primary efficacy endpoint was defined as the proportion of patients achieving an Investigator Global Assessment (IGA) of 0 (clear) or 1 (almost clear) and a decrease of at least two points in IGA at Week 8. Secondary efficacy variables included IGA measurements, pruritus (obtained from the Scoring of Atopic Dermatitis [SCORAD] visual analog scale [VAS]), Eczema Area and Severity Index [EASI], body surface area (BSA), Patient-Oriented Eczema Measure (POEM), Dermatology Life Quality Index (DLQI) and SCORAD.

There was a trend toward a statistically significant higher number of patients who achieved an IGA score of 0 or 1 and a 2 point drop in the DS107 capsules group at Week 8 in comparison to Placebo: 11 (21.6%) Responders in the DS107 capsules group, and 6 (11.8%) in the Placebo group (p-value: 0.057). A similar trend was also observed in the number of patients achieving a decrease of at least 2 points in the IGA score at Week 8 with 14 (27.5%) in the DS107 capsules group and 8 (15.7%) in the Placebo group (p-value: 0.065).

Further analysis was performed on the severity groups (Moderate and Severe/Very Severe at baseline) comparing the DS107 capsules group to the Placebo group in terms of Responders, using the CMH test stratified for Site. The proportion of Responders was always greater in the DS107 capsules group compared to the Placebo group in both the moderate and the severe/very severe populations.

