2.2.4 Study Populations for Analysis

2.2.4.1 Full Analysis Set (FAS)

The FAS consists of all patients who are randomized to the study and received at least one dose of study medication. FAS is the primary analysis population for efficacy endpoints. Analysis will be done according to the treatment patients were randomized to.

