2.2.6 Methods for Handling Missing Data

PROC GENMOD will be used to account for any missing data and early withdrawal for FAS.

The GENMOD procedure will estimate the working correlation from data containing both types of missing values by using the *all available pairs* method, in which all non-missing pairs of data are used in the moment estimators of the working correlation parameters. The resulting covariances and standard errors are valid under the missing completely at random (MCAR) assumption.

A sensitivity analysis will be performed for the Week 8/Exit outcome under the missing at not random (MNAR) assumption for the primary efficacy analyses using the FAS. An extreme analysis will be used to identify the possible outcome considering two scenarios: An extreme analysis will be used to identify the possible outcome considering the worst case for both active treatments and best case for vehicle (Scenario 1) and then the reverse (Scenario 2). If any extreme cases result in statistical significance, then the maximum degree of relaxation per

treatment group still reaching statistical significance will be displayed for each scenario. A two-sided Fisher Exact Test will be utilized for these analyses.

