2.2.12 Efficacy Analyses

Summary statistics by visit will be provided for all efficacy endpoints. For continuous efficacy endpoints, summary statistics will also be provided for change from baseline at each post-baseline visit. Results for the primary and secondary efficacy endpoints will be presented separately for moderate and severe AD as well as combined across moderate and severe AD strata. Models will include a baseline covariate for moderate/severe for all primary and secondary efficacy analyses. Models will be performed for the primary efficacy endpoint for the separate AD strata but not for the secondary efficacy endpoints.

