2.2.12.1 Primary Endpoint

The primary efficacy variable will be the proportion of patients achieving an IGA score of 0 (clear) or 1 (almost clear) and a decrease of at least 2 points in IGA from baseline to week 8. This is a binary endpoint.

The primary endpoint will be analyzed using a Generalised Linear Model (PROC GENMOD) with treatment arm, moderate/severe AD, baseline IGA value, visit and DS treatment dose as factors. The primary analysis will be based on the FAS and repeated for the PPS as a supportive analysis.

This analysis will be performed using SAS PROC GENMOD with code similar to the following:

```
proc genmod data=subjresults descending;  
  class trt visit subj AD;  
  model outcome=trt visit trt*visit AD B_IGA /dist=bin;  
  repeated subject=subj/corr=unstr;  
  slice trt*visit / sliceby=visit ilink cl diff;  
run;
```

where fas= Full Analysis Set (FAS), outcome= patients in each treatment arm at week 8 who achieve an IGA score of 0 (clear) or 1 (almost clear) and a decrease of at least 2 points in IGA from baseline. B_IGA is the baseline IGA value.. The dist=bin option of the model statement specifies that the logit transformation will be applied to outcome prior to analysis. The cl option specifies that two-sided 95% confidence intervals will be provided and the ilink option specifies the transformation from the logit scale to the probability scale. The between-treatment effects are determined from the diff option of the slice statement. Results will be presented separately for moderate and severe AD for both the FAS and PPS populations. The model will be used to estimate Week 8 effect.

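### A patient with no Week 8 IGA drops out of both the tabulated and the modelled response rate, and no SAP analysis counts such patients as non-responders in every arm

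*SAP*

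**What the plan says.** - **Tables.** SAP Appendix A opens: "The following specifications will be used in the production of tables and listings". Its section 4.2 sets the default that "the number of subjects with non-missing data will be used as the denominator for the calculation of the percentages, unless otherwise noted". Section 4 of the appendix puts the analysis population's name under each table title. SAP 2.2.12 adds: "Summary statistics by visit will be provided for all efficacy endpoints". Neither document notes another denominator for IGA response.
- **Population.** SAP 2.2.4.1 defines the FAS as everyone randomised and dosed at least once, and says that "FAS is the primary analysis population for efficacy endpoints".
- **Primary analysis.** SAP 2.2.12.1 fits a repeated-measures binomial model with treatment, visit, their interaction and baseline severity terms. "The model will be used to estimate Week 8 effect".
- **Missing data.** SAP 2.2.6 relies on GENMOD's all-available-pairs method and describes the covariances and standard errors as valid under MCAR. Protocol 12.9.2 assumes missing at random (MAR) and plans a jump-to-reference analysis with placebo as reference. The SAP does not carry that analysis over.
- **Sensitivity analysis.** SAP 2.2.6 tests two extremes for the Week 8/Exit outcome with Fisher's exact test. One sets every missing outcome against the active arms and in favour of placebo, and the other does the opposite. If an extreme is significant, the SAP will show how far the assumption can be relaxed.
- **Exits.** Protocol 6.1 anticipates patients leaving in the first four weeks for apparent lack of efficacy, and 7.5.2 lists lack of efficacy as a reason for stopping study drug. Under 7.5, patients who discontinue early are asked to attend an early-termination visit with the Week 8 assessments.

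**The concern.** The endpoint is a proportion of patients, and the FAS is meant to keep every treated patient in that proportion. Under the plan, a patient who leaves without a Week 8 or early-termination IGA counts in the FAS but appears in neither the Week 8 percentage nor the Week 8 data of the model. If people leave because treatment is not working, those who remain are a favourable selection, and the rate among them overstates the rate among all treated patients. If the arms lose patients at different rates, the treatment difference shifts as well. The reader of the report would need one moderate analysis, using the same rule in every arm, to judge how much this matters. The SAP offers only the two extremes.

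**Working it through.** **1. The plan's own figures.** Protocol 12.3 gives 45% power for 21.6% v 11.8% with 100 evaluable patients per arm, two-sided 5%. With pooled variance under the null, p̄ = 0.167:

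z = [0.098 × √100 − 1.96 × √(2 × 0.167 × 0.833)] / √(0.216 × 0.784 + 0.118 × 0.882) = (0.980 − 1.034) / 0.523 = −0.103, so power = 45.9%.

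This reproduces the stated figure. The SAP's 10% plus 15 points gives 80.2% power at 100 per arm. Neither figure depends on the denominator rule, so the sample-size arithmetic is not in dispute here.

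**2. Effect of the denominator.** If a share d of an arm has no Week 8 IGA and none of those patients responds, the observed-case rate is the all-patient rate divided by (1 − d). The documents give no d. Assume 20 responders of 100 on drug and 12 of 100 on placebo:

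| Missing, drug / placebo | Drug | Placebo | Difference (points) |
|---|---|---|---|
| all FAS patients counted | 20/100 = 20.0% | 12/100 = 12.0% | 8.0 |
| 15% / 15% | 20/85 = 23.5% | 12/85 = 14.1% | 9.4 |
| 20% / 10% | 20/80 = 25.0% | 12/90 = 13.3% | 11.7 |
| 10% / 20% | 20/90 = 22.2% | 12/80 = 15.0% | 7.2 |

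Under MCAR the observed-case rates are right in expectation. Counting missing as failure would then be too low: at d = 20%, 0.8 × 21.6 = 17.3% and 0.8 × 11.8 = 9.4%.

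**3. Does the model repair this?** A GEE model was fitted to one simulated arm of 4,000 patients with four visits, of whom 20% lost Week 8:

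| Dropout | Full data | Observed cases | Model, Week 8 |
|---|---|---|---|
| MCAR | 18.3% | 17.8% | 17.8% |
| Only Week 8 non-responders | 17.3% | 21.7% | 21.0% (exchangeable) to 21.7% (independence) |

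The model rate follows the observed-case rate. The check did not run the SAP's unstructured correlation or its covariates, so it shows the direction and not an exact size.

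**4. Do the two extremes help?** Take 100 per arm with exactly m missing in each, and let observed responders be binomial on 100 − m. In the first scenario, drug has X of 100 and placebo has Y + m of 100. In the second, drug has X + m and placebo has Y. Summing the exact binomial probabilities over all outcomes where a two-sided Fisher test at 5% favours drug gives:

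| m | First scenario, true 21.6% v 11.8% | Second scenario, true 11.8% in both arms |
|---|---|---|
| 0 | 39.5% | 1.5% |
| 5 | 6.9% | 11.6% |
| 10 | 0.3% | 42.4% |
| 20 | 0.0% | 97.3% |

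From 10% missing, the first scenario almost never supports a drug that works as in Phase 2a, and the second often supports a drug that does nothing. Even at the SAP's assumed 25% v 10%, the first succeeds in under 4% of trials at m = 10.

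**The case against.** Several stronger readings are tempting, and the documents do not support them.

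- **The table rule defines the primary proportion.** It does not. It is an overridable formatting default for tables, and the primary result is a model estimate. Changing the table alone would leave the primary p-value untouched. The table and the model share a weakness because neither has Week 8 data for these patients.
- **All dropouts are lost.** They are not. Early-termination visits include the IGA, SAP 2.2.5 dates Visit 6 earlier for patients who discontinue, and patients may stop drug and stay in follow-up. But attendance is only requested, and Protocol 7.5.1 ends all evaluations for complete withdrawals. The gap shrinks without closing.
- **Inflation is certain.** It requires missing patients to respond less often than observed ones. The protocol's own expectation of exits for lack of efficacy makes this plausible, not proven.
- **No planned analysis counts missing as failure.** The first extreme does so for both active arms, and the reverse does so for placebo. There is also the conditional relaxation step, and SAP 2.2.12.2 plans response at the last treatment visit. None of these applies missing = non-response to every arm.
- **The rates cannot be compared with Phase 2a.** Protocol 1.6 reports "11 (21.6%) Responders in the DS107 capsules group, and 6 (11.8%) in the Placebo group". 11/51 = 21.6% and 6/51 = 11.8%, and 51 + 51 is all 102 patients. The documents do not say whether any Week 8 outcome was missing there or how it was handled, and the SAP's sample size rests on other rates.
- **The interim will use inflated rates.** SAP 2.2.10 does not say which rate updates the assumptions. That is a gap to fill, not an error shown.

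One further objection stands in part. Counting missing as failure targets a different quantity from the protocol's primary estimand, which describes the effect under full adherence. That is a reason to keep the new analysis supportive, and it is not a reason to omit it.

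**Conclusion.** The point holds as a gap in the missing-data plan. Both the descriptive and the modelled Week 8 response rates rest on patients with a Week 8 or early-termination IGA, and the SAP claims validity under MCAR and nothing weaker. If those without one respond less often, both rates are too high. The treatment difference can move in either direction, from 8.0 points to between 7.2 and 11.7 in the illustration. That range assumes 10-20% missing and no responders among the missing. The true size cannot be stated from the documents. At 10% missing or more, the SAP's one sensitivity analysis would seldom settle the matter, and the protocol's jump-to-reference analysis is absent from the SAP. Nothing here shows that the primary model must be replaced.

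**What to change.** Keep the primary model and make three additions before unblinding:

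1. In SAP 2.2.6 and 2.2.12.1, add one supportive Week 8 analysis on the FAS that counts a missing Week 8 IGA as non-response in every arm, with the same covariates as the primary model. State that an early-termination IGA recorded at Visit 6 counts as data.
2. In the Week 8 response table, show responders over all FAS patients beside the observed-case percentage, and note this as the exception that Appendix A 4.2 allows.
3. In SAP 2.2.10, state which of the two rates the interim uses.

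The cost is one table column, one extra model run and one sentence on the interim. The supportive rate will be conservative (too low) if data are in fact missing at random, and the report should say so.
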